Eating and digestion subscore at Vi Calculated for Vi = {Baseline, W6, W14, M6, M9, M12}	If at least 2 of the following items are answered, Scores are linearly transformed to a 0-100 scale where 0 means all answered items were a "0" and "100" means that all answered items were a "4" Items: Difficulty swallowing solid foods, Difficulty swallowing liquids, Vomiting and Weight loss Missing otherwise
Muscles and joints subscore at Vi Calculated for Vi = {Baseline, W6, W14, M6, M9, M12}	If at least 2 of the following items are answered, Scores are linearly transformed to a 0-100 scale where 0 means all answered items were a "0" and "100" means that all answered items were a "4" Items: Joint and muscle aches, Limited joint movement, Muscle cramps and Weak muscles Missing otherwise

Energy subscore at Vi Calculated for Vi = {W6, W14, M6, M9, M12}
	
If at least 2 of the following items are answered, Scores are linearly transformed to a 0-100 scale where 0 means all answered items were a “0” and “100” means that all answered items were a “4”
 
Items: Loss of energy, Need to sleep more/take naps and Fevers
 
Missing otherwise

Mental and emotional subscore at Vi Calculated for Vi = {Baseline, W6, W14, M6, M9, M12}
	
If at least 2 of the following items are answered, Scores are linearly transformed to a 0-100 scale where 0 means all answered items were a “0” and “100” means that all answered items were a “4”
 
Items: Depression, Anxiety and Difficulty sleeping
 
Missing otherwise

Global Lee symptom scale score at Vi Calculated for Vi = {Baseline, W6, W14, M6, M9, M12}
	
The global score is defined as the average of subscores, if at least 4 are available.
 
Missing otherwise

Subscale score - Change from baseline at Vi Calculated for Vi = {W6, W14, M6, M9, M12} and for skin, eyes and mouth, breathing, eating and digestion, muscles and joints, energy, mental and emotional subscores
	
Subscale score at Vi – Subscale score at baseline
 
Missing if the subscore is missing at Vi and/or baseline

Global Lee symptom scale score - Change from baseline at Vi Calculated for Vi = {W6, W14, M6, M9, M12}
	
Global Lee score at Vi – Global Lee score at baseline
 
Missing if the global Lee score is missing at Vi and/or baseline

The following table will be presented:

Variable	Visit	Statistics / Modality	FAS Population (N = XX)

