First subscore	Baseline	N (N Missing)	XX (XX)
		Mean ± SD	XX.X ± XX.X
		Median [Min ; Max]	XX [XX ; XX]
		CI 95%	[XX.X ; XX.X]
	W6	N (N Missing)	XX (XX)
		Mean ± SD	XX.X ± XX.X
		Median [Min ; Max]	XX [XX ; XX]
		CI 95%	[XX.X ; XX.X]
	W14	N (N Missing)	XX (XX)
		Mean ± SD	XX.X ± XX.X
		Median [Min ; Max]	XX [XX ; XX]
		CI 95%	[XX.X ; XX.X]
	M6	N (N Missing)	XX (XX)
		Mean ± SD	XX.X ± XX.X
		Median [Min ; Max]	XX [XX ; XX]
		CI 95%	[XX.X ; XX.X]
	M9	N (N Missing)	XX (XX)
		Mean ± SD	XX.X ± XX.X
		Median [Min ; Max]	XX [XX ; XX]
		CI 95%	[XX.X ; XX.X]
	M12	N (N Missing)	XX (XX)
		Mean ± SD	XX.X ± XX.X
		Median [Min ; Max]	XX [XX ; XX]
		CI 95%	[XX.X ; XX.X]
First subscore – Change from baseline	W6	N (N Missing)	XX (XX)
		Mean ± SD	XX.X ± XX.X
		Median [Min ; Max]	XX [XX ; XX]
		CI 95%	[XX.X ; XX.X]
	W14	N (N Missing)	XX (XX)
		Mean ± SD	XX.X ± XX.X
		Median [Min ; Max]	XX [XX ; XX]
		CI 95%	[XX.X ; XX.X]
	M6	N (N Missing)	XX (XX)
		Mean ± SD	XX.X ± XX.X
		Median [Min ; Max]	XX [XX ; XX]
		CI 95%	[XX.X ; XX.X]
	M9	N (N Missing)	XX (XX)
		Mean ± SD	XX.X ± XX.X
		Median [Min ; Max]	XX [XX ; XX]

	CI 95%	[XX.X ; XX.X]
M12	N (N Missing)	XX (XX)
	Mean ± SD	XX.X ± XX.X
	Median [Min ; Max]	XX [XX ; XX]
	CI 95%	[XX.X ; XX.X]

This table will be completed for:

- Skin subscore
- Eyes and mouth subscore
- Breathing subscore
- Eating and digestion subscore
- Energy subscore
- Mental and emotional subscore
- Global Lee symptom scale score

Global score and each subscore over time will be graphically represented by boxplots.

The change from baseline over time of the global score and each subscore will be graphically represented by the mean and its associated CI 95%.

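### The Lee Energy subscore has no baseline derivation, so its planned change from baseline cannot be computed and the global change mixes a six-subscore mean with a seven-subscore mean

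*SAP*

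**What the plan says.** In the Lee Symptom Scale derivation table of SAP 11.4.2.4, Skin, Eyes and mouth, Breathing, Eating and digestion, Muscles and joints, and Mental and emotional all carry the visit set "Calculated for Vi = {Baseline, W6, W14, M6, M9, M12". The row "Energy subscore at Vi" carries "Calculated for Vi = {W6, W14, M6, M9, M12" instead, with no Baseline.

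The same table plans a change from baseline for a list of subscores that includes "muscles and joints, energy, mental and emotional subscores", and sets that change to "Missing if the subscore is missing at Vi and/or baseline".

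The global score is itself derived at baseline: "The global score is defined as the average of subscores, if at least 4 are available". Its change is "Global Lee score at Vi – Global Lee score at baseline".

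The table shell that follows has a Baseline row and change-from-baseline rows, and is to be completed for Energy. The figure list in SAP 14.2 (Figures and graphs) includes 14.3.3.2.5b, the Energy change from baseline.

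In both the list of subscores to tabulate and the figure list, the entry for "Eating and digestion subscore" is followed directly by Energy. Muscles and joints, which sits between them in the derivation table, is in neither list. Yet the text below the shell promises plots of every subscore and of its change.

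**The concern.** The derivation table is what a programmer implements, and here it contradicts the outputs it is meant to feed. Two results would go wrong if the Energy row were followed to the letter.

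- The Energy change table rows and figure would be empty.
- The global change would still be produced, but from unlike quantities. The four-subscore minimum is met at baseline without Energy, so nothing is set to missing. The FACT-BMT global score in the same section is missing if any subscore is missing, so the same slip there would show itself.

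Improving quality of life on this scale is a stated secondary objective (Protocol 2.2, SAP 8.1.2). The trial has a single arm, so no comparator would cancel a systematic offset, and a larger sample would not shrink it.

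**Working it through.** The documents give no figure to reproduce here, so the check applies the SAP's own rules.

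**Subscores available with complete data** (visit sets in SAP 11.4.2.4)
- Baseline: 6 (Energy absent). This passes the minimum of 4, so a global score is computed.
- W6, W14, M6, M9, M12: 7 each.
- Energy changes from baseline that can be computed: 0 at all five visits.

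If other subscores are missing the counts vary, but Energy is never in the baseline average.

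**Offset in the global change**
Let M be the mean of the other six subscores and E the Energy subscore, with suffix b for baseline and f for follow-up.
- As written: change = (6·Mf + Ef)/7 − Mb
- With Energy scored at baseline: change = (6·Mf + Ef)/7 − (6·Mb + Eb)/7
- Difference: (6·Mb + Eb)/7 − Mb = (Eb − Mb)/7

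With complete data the offset depends only on the patient's baseline values and is the same at all five visits. Higher Lee scores mean worse symptoms (SAP 17.3), so a positive offset looks like worsening.

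**Range under assumed scores** (the documents contain no Lee values)
- Lowest, Mb = 30 and Eb = 0: (0 − 30)/7 = −4.3
- Highest, Mb = 10 and Eb = 100: (100 − 10)/7 = +12.9
- Eb = 50 with Mb = 10, 20, 30: +5.7, +4.3, +2.9
- Eb = Mb: 0

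**What this does to a reported change** (assumed Mb = 20, Eb = 50)
- No true change: as written (6·20 + 50)/7 − 20 = +4.29; corrected 0.
- All seven subscores fall by 5: as written (6·15 + 45)/7 − 20 = −0.71; corrected −5.00.
- Energy alone falls by 10: as written (6·20 + 40)/7 − 20 = +2.86; corrected 22.86 − 24.29 = −1.43.

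**Derived subscores against the named lists**
The derivation table has seven subscores. The table list and the figure list each name six plus the global score. The only one absent, from both, is Muscles and joints.

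**The case against.** The strongest reply is that this is a drafting slip with an obvious intent. The change list, the table shell and figure 14.3.3.2.5b all presuppose a baseline Energy score. The scale is completed at selection or inclusion (Protocol Table 2 and 8.3, SAP 9.4.1). A careful programmer would query the row. All of that stands. It makes this an internal inconsistency, not a deliberate analysis choice, and the wrong results follow only if the row is programmed literally. It does not remove the need to correct the row, because the error in the global score would raise no flag.

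The stakes are also limited. Protocol 9.1.2 makes quality of life a descriptive endpoint, and Protocol 9.2 keeps patient-reported outcomes out of response decisions. The SAP plans no test on the Lee scale.

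Three stronger readings are tempting but not supported.

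- **That Muscles and joints is never reported.** The sentences on plots of every subscore would cover it, the title of Table 14.3.4.2 is generic, and the subscore enters the global score. What the documents show is a conflict between the named lists and that text.
- **That the offset makes patients look worse, or amounts to a given share of a meaningful change.** Its sign depends on whether Energy lies above or below the other subscores at baseline, which is unknown. SAP 17.3 defines a meaningful difference as half the baseline standard deviation, but no standard deviation is given and 11.4.2.4 does not apply the threshold.
- **That SAP 17.3 already resolves the matter.** It defines a different set of seven subscales, with the muscle and joint items inside a seven-item Energy subscale. It sets no visits, so adopting it would settle the Muscles and joints listing but would not supply the missing Energy baseline.

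**Conclusion.** The inconsistency is real and minor. Followed as written, SAP 11.4.2.4 yields no Energy change from baseline at any visit. With complete data its global Lee change is offset by (Eb − Mb)/7. That formula follows from the stated rules alone. The range of −4.3 to +12.9 points rests on assumed scores and shows only that the offset could be either negligible or large enough to hide or reverse a modest true change. The listing of Muscles and joints is a second, smaller inconsistency in the same section. The primary endpoint, the sample size and the response assessments are unaffected.

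**What to change.** Add Baseline to the visit set of the Energy row. This restores seven subscores at every visit with complete data and removes the offset.

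Then state whether the subscales of 11.4.2.4 or those of 17.3 apply, and make the named table and figure lists match. If 11.4.2.4 stands, Muscles and joints joins both lists. If 17.3 stands, the derivation rows and both lists must be rewritten to its subscales, each with Baseline in its visit set. The lists should not be completed before that choice is made.

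No new scoring rule is needed. Restricting the global change to subscores present at both visits would depart from the section's own definition, and the reported change could then differ from the difference between the reported global scores.

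The cost is SAP wording and the matching program lines. The questionnaire is already completed at inclusion, so no further data are required.

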11.4.2.5 Assessment of chronic GvHD activity post-ATO treatment

Chronic GvHD activity (global and by organ) will be reported at 6 weeks, 14 weeks, 6, 9 and 12 months after the first infusion of ATO.

- **Global chronic GvHD activity**

Variable	Modality	FAS Population (N = XX)
Health care provider global ratings		
W6	None	n/N (XX.XX%)
	Mild	n/N (XX.XX%)
	Moderate	n/N (XX.XX%)
	Severe	n/N (XX.XX%)
	Missing	n
W14	None	n/N (XX.XX%)
	Mild	n/N (XX.XX%)
	Moderate	n/N (XX.XX%)
	Severe	n/N (XX.XX%)

	Missing	n
M6	None	n/N (XX.XX%)
	Mild	n/N (XX.XX%)
	Moderate	n/N (XX.XX%)
	Severe	n/N (XX.XX%)
	Missing	n
M9	None	n/N (XX.XX%)
	Mild	n/N (XX.XX%)
	Moderate	n/N (XX.XX%)
	Severe	n/N (XX.XX%)
	Missing	n
M12	None	n/N (XX.XX%)
	Mild	n/N (XX.XX%)
	Moderate	n/N (XX.XX%)
	Severe	n/N (XX.XX%)
	Missing	n

Stacked bar graphs will be used for illustrating the percentage of patients in each score category at each time points (6 weeks, 14 weeks, 6, 9 and 12 months after the first infusion of ATO).

- **Chronic GvHD activity for each organ**
 - **Derivation**

Derived variables	Definition
Mouth score	
For each visit of interest, sum of the 3 following scores:
 
 - Erythema (MOUTH1) - Lichenoid (MOUTH2) - Ulcers (MOUTH3) 
Missing if at least one missing score
 
Score to be calculated for the following visits: W6, W14, M6, M9 and M12

The following table will be presented:

Organ score	Visit	Statistics / Modality	FAS Population (N=XX)
Organ – Abnormalities present but explained entirely by non-GvHD documented cause	W6	No	n/N (XX.X%)
		Yes	n/N (XX.X%)
		Missing	n
Categorical score	W6	Modality 1	n/N (XX.XX%)
	
		Modality n	n/N (XX.XX%)
		Missing	n
Organ – Abnormalities present but explained entirely by non-GvHD documented cause	W14	No	n/N (XX.X%)
		Yes	n/N (XX.X%)
		Missing	n
Categorical score	W14	Modality 1	n/N (XX.XX%)
	
		Modality n	n/N (XX.XX%)
		Missing	n
Organ – Abnormalities present but explained entirely by non-GvHD documented cause	M6	No	n/N (XX.X%)
		Yes	n/N (XX.X%)
		Missing	n
Categorical score	M6	Modality 1	n/N (XX.XX%)
	
		Modality n	n/N (XX.XX%)
		Missing	n
Organ – Abnormalities present but explained entirely	M9	No	n/N (XX.X%)
		Yes	n/N (XX.X%)
		Missing	n

by non-GvHD documented cause

Categorical score	M9	Modality 1 ... Modality n Missing	n/N (XX.XX%) ... n/N (XX.XX%) n
Organ – Abnormalities present but explained entirely by non-GvHD documented cause	M12	No Yes Missing	n/N (XX.X%) n/N (XX.X%) n
Categorical score	M12	Modality 1 ... Modality n Missing	n/N (XX.XX%) ... n/N (XX.XX%) n
Liver – Abnormalities present but explained entirely by non-GvHD documented cause	W6	No Yes Missing	n/N (XX.X%) n/N (XX.X%) n
Total bilirubin*	W6	N (N Missing) Mean ± SD Median [Min ; Max]	XX (XX) XX.X ± XX.X XX [XX ; XX]
SGPT*	W6	N (N Missing) Mean ± SD Median [Min ; Max]	XX (XX) XX.X ± XX.X XX [XX ; XX]
ALK*	W6	N (N Missing) Mean ± SD Median [Min ; Max]	XX (XX) XX.X ± XX.X XX [XX ; XX]
Lung – Abnormalities present but explained entirely by non-GvHD documented cause	W6	No Yes Missing	n/N (XX.X%) n/N (XX.X%) n
FEV1**	W6	N (N Missing) Mean ± SD	XX (XX) XX.X ± XX.X

		Median [Min ; Max]	XX [XX ; XX]
Liver – Abnormalities present but explained entirely by non- GvHD documented cause	W14	No	n/N (XX.X%)
		Yes	n/N (XX.X%)
		Missing	n
Total bilirubin*	W14	N (N Missing) Mean ± SD	XX (XX) XX.X ± XX.X
		Median [Min ; Max]	XX [XX ; XX]
SGPT*	W14	N (N Missing) Mean ± SD	XX (XX) XX.X ± XX.X
		Median [Min ; Max]	XX [XX ; XX]
ALK*	W14	N (N Missing) Mean ± SD	XX (XX) XX.X ± XX.X
		Median [Min ; Max]	XX [XX ; XX]
Lung – Abnormalities present but explained entirely by non- GvHD documented cause	W14	No	n/N (XX.X%)
		Yes	n/N (XX.X%)
		Missing	n
FEV1**	W14	N (N Missing) Mean ± SD	XX (XX) XX.X ± XX.X
		Median [Min ; Max]	XX [XX ; XX]
Liver – Abnormalities present but explained entirely by non- GvHD documented cause	M6	No	n/N (XX.X%)
		Yes	n/N (XX.X%)
		Missing	n
Total bilirubin*	M6	N (N Missing) Mean ± SD	XX (XX) XX.X ± XX.X
		Median [Min ; Max]	XX [XX ; XX]
SGPT*	M6	N (N Missing) Mean ± SD	XX (XX) XX.X ± XX.X
		Median [Min ; Max]	XX [XX ; XX]
ALK*	M6	N (N Missing) Mean ± SD	XX (XX) XX.X ± XX.X
		Median [Min ; Max]	XX [XX ; XX]
Lung – Abnormalities present but explained entirely by non- GvHD documented cause	M6	No	n/N (XX.X%)
		Yes	n/N (XX.X%)
		Missing	n
FEV1**	M6	N (N Missing) Mean ± SD	XX (XX) XX.X ± XX.X
		Median [Min ; Max]	XX [XX ; XX]

Liver – Abnormalities present but explained entirely by non- GvHD documented cause	M9	No	n/N (XX.X%)
		Yes	n/N (XX.X%)
		Missing	n
Total bilirubin*	M9	N (N Missing) Mean ± SD Median [Min ; Max]	XX (XX) XX.X ± XX.X XX [XX ; XX]
SGPT*	M9	N (N Missing) Mean ± SD Median [Min ; Max]	XX (XX) XX.X ± XX.X XX [XX ; XX]
ALK*	M9	N (N Missing) Mean ± SD Median [Min ; Max]	XX (XX) XX.X ± XX.X XX [XX ; XX]
Lung – Abnormalities present but explained entirely by non- GvHD documented cause	M9	No	n/N (XX.X%)
		Yes	n/N (XX.X%)
		Missing	n
FEV1**	M9	N (N Missing) Mean ± SD Median [Min ; Max]	XX (XX) XX.X ± XX.X XX [XX ; XX]
Liver – Abnormalities present but explained entirely by non- GvHD documented cause	M12	No	n/N (XX.X%)
		Yes	n/N (XX.X%)
		Missing	n
Total bilirubin*	M12	N (N Missing) Mean ± SD Median [Min ; Max]	XX (XX) XX.X ± XX.X XX [XX ; XX]
SGPT*	M12	N (N Missing) Mean ± SD Median [Min ; Max]	XX (XX) XX.X ± XX.X XX [XX ; XX]
ALK*	M12	N (N Missing) Mean ± SD Median [Min ; Max]	XX (XX) XX.X ± XX.X XX [XX ; XX]
Lung – Abnormalities present but explained entirely by non- GvHD documented cause	M12	No	n/N (XX.X%)
		Yes	n/N (XX.X%)
		Missing	n
FEV1**	M12	N (N Missing) Mean ± SD Median [Min ; Max]	XX (XX) XX.X ± XX.X XX [XX ; XX]

* Chemistry associated to liver, ** Linked to lung function

This table will be completed for the following scores:

Organ	Score
Skin	Score 0: No BSA involved Score 1: 1-18% BSA Score 2: 19-50% BSA Score 3: > 50% BSA
Skin features score	Score 0: No sclerotic features Score 2: Superficial sclerotic features "not hidebound" (able to pinch) Score 3: Deep sclerotic features, "Hidebound" (unable to pinch), Impaired mobility, Ulceration
Mouth - Erythema	None Mild erythema or moderate erythema (<25%) Moderate (>=25%) or severe erythema (<25%) Severe erythema (>= 25%)
Mouth - Lichenoid	None Lichen-like changes (<25%) Lichen-like changes (25-50%) Lichen-like changes (>50%)
Mouth - Ulcers	None Ulcers involving (<=20%) Severe ulcerations (>20%)
Eyes	Score 0: No symptoms Score 1: Mild dry eye symptoms not affecting ADL Score 2: Moderate dry eye symptoms partially affecting ADL without new vision impairment due to KCS Score 3: Severe eye symptoms significantly affecting ADL or unable to work because of ocular symptoms of loss or vision due to KCS
Gastro-intestinal (Esophageal)	0 = No esophageal symptoms

	
1 = Occasional dysphagia or odynophagia with solid foods or pills during the past week
 
2 = Intermittent dysphagia or odynophagia with solid foods or pills, but not for liquids or soft foods, during the past week
 
3 = Dysphagia or odynophagia for almost all oral intake, on almost every day of the past week

Gastro-intestinal (Upper)	
0 = No symptoms
 
1 = Mild, occasional symptoms, with little reduction in oral intake during the past week
 
2 = Moderate, intermittent symptoms, with some reduction in oral intake during the past week
 
3 = More severe or persistent symptoms throughout the day, with marked reduction in oral intake, on almost every day of the past week

Gastro-intestinal (Lower)	
0 = No loose or liquid stools during the past week
 
1 = Occasional loose or liquid stools, on some days during the past week
 
2 = Intermittent loose or liquid stools throughout the day, on almost every day of the past week, without requiring intervention to prevent or correct volume depletion
 
3 = Voluminous diarrhea on almost every day of the past week, requiring intervention to prevent or correct volume depletion

Joint and fascia	Score 0: No symptoms

	
Score 1: Mild tightness of arms or legs, normal or mild decreased range of motion and not affecting ADL
 
Score 2: Tightness of arms or legs OR joint contractures, erythema thought due to fasciitis, moderate decrease ROM AND mild to moderate limitation of ADL
 
Score 3 : Contractures WITH significant decrease of ROM AND significant limitation of ADL (unable to tie shoes, button shirts, dress self, etc.)

Lungs	
Score 0: No symptoms
 
Score 1: Mild symptoms (shortness of breath after climbing one flight of steps)
 
Score 2: Moderate symptoms (shortness of breath after walking on flat ground)
 
Score 3: Severe symptoms (shortness of breath at rest, requiring O2)

This table will be also presented on PP population.

Stacked bar graphs will be used for illustrating the percentage of patients in each score category at each time points (6 weeks, 14 weeks, 6, 9 and 12 months after the first infusion of ATO).

Continuous indicators will be represented by boxplots.

- **Physician assessment of current overall chronic GvHD severity**

Variable	Statistics	FAS Population (N = XX)
Chronic GVHD severity from 0 (not at all) to 10 (the most severe)		
W6	N (N Missing) Mean \pm SD Median [Min ; Max]	XX (XX) XX.X \pm XX.X XX [XX ; XX]
W14	N (N Missing) Mean \pm SD	XX (XX) XX.X \pm XX.X

	Median [Min ; Max]	XX [XX ; XX]
M6	N (N Missing)	XX (XX)
	Mean ± SD	XX.X ± XX.X
	Median [Min ; Max]	XX [XX ; XX]
M9	N (N Missing)	XX (XX)
	Mean ± SD	XX.X ± XX.X
	Median [Min ; Max]	XX [XX ; XX]
M12	N (N Missing)	XX (XX)
	Mean ± SD	XX.X ± XX.X
	Median [Min ; Max]	XX [XX ; XX]

Physician evaluations of current overall chronic GvHD severity over time will be graphically represented by boxplots.

- **Physician evaluations of chronic GvHD changes**

Variable	Statistics	FAS Population (N = XX)
Over the time would you say that this patient's GVHD is...		
W6	N (N Missing)	XX (XX)
	Mean ± SD	XX.X ± XX.X
	Median [Min ; Max]	XX [XX ; XX]
W14	N (N Missing)	XX (XX)
	Mean ± SD	XX.X ± XX.X
	Median [Min ; Max]	XX [XX ; XX]
M6	N (N Missing)	XX (XX)
	Mean ± SD	XX.X ± XX.X
	Median [Min ; Max]	XX [XX ; XX]
M9	N (N Missing)	XX (XX)
	Mean ± SD	XX.X ± XX.X
	Median [Min ; Max]	XX [XX ; XX]
M12	N (N Missing)	XX (XX)
	Mean ± SD	XX.X ± XX.X
	Median [Min ; Max]	XX [XX ; XX]

Physician evaluations of chronic GvHD changes over time will be graphically represented by boxplots.

12. SAFETY EVALUATION

12.1 ADVERSE EVENTS

All treatment related toxicities and other AE and SAE occurring from the time of signed informed consent until the end of the study are recorded. They are coded using the Medical Dictionary for Regulatory Activities (MedDRA) and classified according to the NCI common toxicity criteria (CTC), specification for stem cell transplantation.

A SAE or serious adverse drug reaction is any untoward medical occurrence at any dose that:

- Results in death;
- Is life-threatening (immediate risk of death);
- Requires inpatient hospitalization or prolongation of existing hospitalization for medical reasons (e.g. prolongation of hospitalization for social reasons is excluded);
- Results in persistent or significant disability/incapacity;
- Results in congenital anomaly/birth defect.

The investigator will decide whether the serious adverse event is related to trial medication. The decision will be recorded on the serious adverse event report. The assessment of causality is made by the investigator as not related, unlikely, possibly related or definitely related.

All AE not previously described in the Summary of Product Characteristics of TRISENOX® or in the Investigator Brochure of ARSCIMED® should be considered as unexpected AE.

When calculating the incidence of AEs and SAEs, each subject will only be counted once and any repetitions of AEs will be ignored; the denominator will be the total population size.

Type of AE	Safety Population (N=XX)	N AEs
AE	n/N (XX.X%)	n
Serious AE	n/N (XX.X%)	n
AE leading to death	n/N (XX.X%)	n
AE leading to withdrawal	n/N (XX.X%)	n
Related AE	n/N (XX.X%)	n

Adverse events will be also presented by SOC and PT:

SOC	PT	Safety Population (N=XX)	N AEs
SOC 1	PT 1	n/N (XX.X%)	n
	PT 2	n/N (XX.X%)	n

SOC n	PT 1	n/N (XX.X%)	n
	PT 2	n/N (XX.X%)	n

This table will be presented for each type of AE.

A list of all AEs will be produced in a table including the following items:

- Patient number
- Age at inclusion
- AE names
- AE grade
- Seriousness
- Date of onset first cycle ATO
- Date of end first cycle ATO
- Second cycle ATO (yes/no)
- Date of onset second cycle ATO
- Date of end second cycle ATO

- Relation (causality)
- Action taken for AE
- Date of onset of AE
- Outcome of AE (Resolved without sequelae/ ongoing/ death)

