### **11.2. Reporting Period**

SAEs require immediate notification to Sponsor beginning from the time that the subject provides informed consent, which is obtained prior to the subject's participation in the clinical trial, i.e., prior to undergoing any trial-related procedure and/or receiving investigational medicinal product, through 30 days after the administration of the last dose.

Any SAE occurring any time after the reporting period must be promptly reported if a causal relationship to investigational medicinal product is suspected.

AEs (serious and non-serious) should be recorded on the electronic CRF from the time the subject has taken at least one dose of trial treatment through last subject visit.

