12.4 STATISTICAL ANALYSIS METHODS PLANNED IN THE PROTOCOL AND DETERMINATION OF SAMPLE SIZE

12.4.3 Statistical and Analytical Plans

12.4.3.1 General approaches

All continuous data will be summarized using the following statistics: n (non-missing sample size), mean, standard deviation, median, minimum (min) and maximum (max). All categorical/qualitative data will be presented using the frequency and the percentage of patients who are in the particular category. In general, all data will be listed, sorted by site, subject, and by visit number within subject. All summary tables will be annotated with the total population size relevant to that table/treatment, including any missing observation.

The mean and the standard deviation will be reported to one decimal place greater than the original data. Median, minimum and maximum will use the same number of decimal places as the original data. P-values ≥ 0.001 will be reported to 3 decimal places; p-values less than 0.001 will be reported as “<0.001”.

Type 1 error rate will be set at 0.05.

All statistical analyses will be conducted using SAS version 9.4.

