12.4.3.5 Determination of sample size

The aim of this study is to assess whether ATO allows improving response rate at 6 months after the diagnosis of chronic GVHD from 60% to 85%.

For the sample size calculation in this trial, an A'Hern one stage design has been used (ref 1).

- Let P_0 be the smallest response rate, if true, implies that the role of ATO is too low and therefore the present schedule does not warrant further investigation. In the present trial, P_0 has been taken as 60%.
- Let P_1 be the highest response rate which, if true, implies that the feasibility is sufficiently high and therefore the current schedule warrants further investigation in clinical trials. In the present trial, P_1 has been taken as 85%;
- Let α be the accepted probability of recommending for further investigation a regimen with a true discontinuation rate at least equal to P_0 . In the present trial, α has been taken as 0.05.
- Let β be the accepted probability of rejecting for further investigation a regimen with a true discontinuation rate less than P_1 . In the present trial, β has been taken as 0.20.

The required number of eligible patients is 21. To compensate for a dropout of 10%, 24 patients are planned to be included.

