11. EFFICACY EVALUATION

11.1 ANALYSES POPULATIONS

Every patient included in the study and who has received at least one infusion of ATO will be taken into account at time of data analysis.

The number of patients included who did not receive any infusion of ATO will be reported as well as the reason for not receiving ATO.

The following analyses populations will be considered:

- The safety population consists of all patients included in the study for whom there is any evidence that they used at least one ATO injection.
- The Full Analysis Set (FAS) population consists of included subjects who completed their first cycle of ATO and for whom the response at Week 6 after diagnosis of chronic GvHD has been evaluated.
- The Per Protocol (PP) population will exclude FAS patients with any major protocol deviations that may impact the efficacy analysis. The exclusion of patients from the PP population will be determined during the final data review meeting. Reason(s) for exclusion will be documented for each patient.

The following table will be presented:

Analysis set (N=XX)	
Safety Population	n/N (XX.XX%)
Full Set Analysis Population	n/N (XX.XX%)
Per Protocol Population	n/N (XX.XX%)

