14.4 Safety		
14.4.1 Adverse events		
14.4.1.1	Safety	AEs summary – During treatment (Cycle 1 and/or Cycle 2)
14.4.1.2	Safety	AEs summary - After the last infusion of ATO until 6 months after the first infusion of ATO
14.4.1.3	Safety	AEs summary - From 6 to 12 months after the first infusion of ATO
14.4.1.4	Safety	AEs by SOC/PT
14.4.1.5	Safety	SAEs by SOC/PT
14.4.1.6	Safety	AEs leading to death by SOC/PT
14.4.1.7	Safety	AEs leading to withdrawal by SOC/PT
14.4.1.8	Safety	Related AEs by SOC/PT
14.4.2: Laboratory parameters		
14.4.2.1	Safety	Laboratory parameters by visit – Absolute values
14.4.3: Physical examination		
14.4.3.1	Safety	Physical examination by visit – Absolute values

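### The AE summaries by period use the full Safety population as denominator, so anyone who left follow-up before a period began is counted in it as event-free

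*SAP*

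**What the plan says.** SAP 12.1 counts patients, not events: "each subject will only be counted once and any repetitions of AEs will be ignored". It adds that "the denominator will be the total population size", and its table shell prints n/N under a Safety Population heading. SAP 11.1 defines that population as included patients with "any evidence that they used at least one ATO injection", however long they stayed in the study.

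The table list in SAP 14.4.1 divides the AE summary into three: during treatment (14.4.1.1), "AEs summary - After the last infusion of ATO until 6 months after the first infusion of ATO" (14.4.1.2) and "AEs summary - From 6 to 12 months after the first infusion of ATO" (14.4.1.3). Each is assigned to the Safety population. No number entering a period, person-time rate or time-to-event analysis of AEs is planned.

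Protocol 11.2 has AEs entered on the case report form "from the time the subject has taken at least one dose of trial treatment through last subject visit". SAP 10.1 foresees patients who are no longer in the study at month 12 and tabulates the reasons, one of which is an AE or SAE.

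**The concern.** The period tables invite the question of how much toxicity appears late. A patient who has left before month 6 has no routine AE recording in months 6 to 12, yet enters table 14.4.1.3 in the same way as a patient who was seen at every visit and had no event. The printed percentage is then lower than the rate among patients who could be observed.

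Protocol 10.3 and SAP 12.4.3.4 promise toxicity rates with 95% confidence intervals. The same denominator would pull those intervals down and, when no event is seen, make late toxicity look more firmly excluded than it is. The laboratory and vital-sign shells (SAP 12.2 and 12.3) print N and N missing at each visit, so shrinking follow-up is visible there. The AE shell has nothing equivalent.

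**Working it through.** **The plan's own figures.** The documents state no AE rate. The one attrition figure is in SAP 12.4.3.5: "To compensate for a dropout of 10%, 24 patients are planned to be included". It reproduces: 21/(1 - 0.10) = 23.3, rounded up to 24, so the allowance is 3 of 24 = 12.5%. The 21 comes from the one-stage response design (60% against 85%, success at 17 or more of 21), for which the exact one-sided error is 0.037 and the power 0.803. The 3 is thus an allowance for the month-6 response endpoint.

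**Inputs.** N = 24 treated patients (Protocol 10.2; patients never given ATO are replaced). L = patients who died or left before the period starts; not given, so a range is assumed. k = patients with an event in the period; assumed.

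**Formula.** Printed rate = k/N. Rate among patients under observation at the start = k/(N - L). Ratio of printed to observed = (N - L)/N.

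| L (assumed) | Still in follow-up | Ratio | A 20% observed rate prints as |
|---|---|---|---|
| 0 | 24 | 1.000 | 20.0% |
| 3 | 21 | 0.875 | 17.5% |
| 6 | 18 | 0.750 | 15.0% |

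**Example with k = 4 (assumed), exact 95% intervals.**
- 4/24 = 16.7% (4.7 to 37.4)
- 4/21 = 19.0% (5.4 to 41.9)
- 4/18 = 22.2% (6.4 to 47.6)

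**Zero events.** The upper 95% limit is 1 - 0.025^(1/n): 14.2% for n = 24, 16.1% for n = 21, 18.5% for n = 18.

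**Separating deaths from withdrawals.** Let L = D + W, with D dead and W alive but unobserved. Suppose the target is the proportion of all treated patients with an event in the window. Deaths then belong in the denominator, since those patients had no event in that window. If withdrawn patients carry the same risk as those observed (assumption), the target is [k/(N - L)] × (N - D)/N, and the printed k/N is (N - L)/(N - D) of it.
- L = 3, all deaths: 21/21 = 1, no dilution.
- L = 3, all withdrawals: 21/24 = 0.875.
- L = 6, three of each: 18/21 = 0.857.

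**Which table is affected.** Table 14.4.1.2 opens at each patient's own last infusion, so few patients can have gone before it starts. The effect falls mainly on table 14.4.1.3.

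**Period lengths.** Elapsed days, using the example schedule and the SAP's 30.5-day month: month 6 is 6 × 30.5 = 183 days. The last infusion of one cycle falls 23 days after the first. With a second cycle begun at 8 to 11 weeks it falls at 56 + 23 = 79 to 77 + 23 = 100 days. The middle period is therefore 183 - 23 = 160 days after one cycle and 83 to 104 days after two, against 183 days for months 6 to 12.

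**The case against.** Five arguments go the other way.

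- **Total N is a legitimate quantity.** It gives the share of treated patients with an event in the window. For deaths this stands: full N is a different estimand and not a mistake. It does not cover patients who are alive but no longer observed.
- **The SAP may allow a table-specific N.** SAP 12.4.3.1 says "All summary tables will be annotated with the total population size relevant to that table/treatment, including any missing observation", and the sentence in 12.1 does not mention periods. But 12.1 is the specific rule for AEs, and the table list names Safety for all three summaries with no count of patients still followed. If another N is intended, the SAP should say so.
- **Recording does not stop completely.** Under Protocol 11.2 an SAE suspected to be related must be reported even after the reporting period, and SAP 12.1 speaks of recording to the end of the study. It would therefore be too strong to infer that a patient who has left can no longer have any event recorded. This limits the problem for related SAEs, but less so for other AEs.
- **Losses may be few.** SAP 12.4.3.2 expects close follow-up after transplantation, and Protocol 10.4.2 keeps following patients who stop ATO for toxicity. With no early losses the effect is zero.
- **The figures can be recomputed.** Listings of study completion, visit dates and AE onset are planned. That helps a later reader, but the planned percentages remain as they are.

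**Conclusion.** The point holds in a limited form. As written, the SAP dilutes the late AE and SAE percentages by (24 - L)/24 relative to the rate among patients under observation, and early losses can only move them in that direction. The size rests on L, which the documents do not give: nil at L = 0, 0.875 at L = 3, 0.75 at L = 6, the last two being assumptions.

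Two stronger readings are tempting. A reader might take the three extra patients in the sample size as the plan's forecast of loss from AE follow-up, and conclude that late toxicity will be understated by 12.5% or more. The documents do not support this: the allowance belongs to the response endpoint, and a patient without an evaluable response may still be followed for AEs. A reader might also infer that a corrected denominator would make the three periods comparable. It would not, because their lengths differ and the middle one varies with the number of cycles.

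In the example the shift from 16.7% to 19.0% is small beside either interval. The tables are descriptive, and the primary efficacy test is unaffected.

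**What to change.** In SAP 12.1, add that for tables 14.4.1.2 and 14.4.1.3 the denominator is the number of Safety patients alive and still in follow-up at the start of the period. Print that number in the column header and show the full-N percentage alongside, so that both quantities can be read. Keep total N for the whole-study tables by system organ class and preferred term. A footnote should state that the periods differ in length and that a patient who leaves during a period still counts as observed throughout it.

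The cost is one added rule in the SAP and one flag per period, derived from dates already collected. Late percentages will come out slightly higher if anyone has left early. Losses within a period remain uncorrected.
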